3.3 NUMBER OF PARTICIPANTS

Up to 200 participants will be enrolled in the control arm and up to 100 participants will be enrolled in the treatment arm for a total of up to 300 participants enrolled in the study.

3.4 INCLUSION CRITERIA

All Participants enrolled into the study must meet the following criteria for entry:

- Adult participants (≥ 18 years of age)
- New diagnosis of OSA
- Prescribed CPAP or APAP for treatment of OSA
- Prescribed a ResMed flow generator compatible with AirView
- Owns a smart phone and is willing to download an app on their phone
- Willing and able to give informed consent
- Can read and comprehend written and spoken English

3.5 EXCLUSION CRITERIA

The participant will be excluded from entry if any of the following criteria apply:

- Have used PAP therapy in the past
- Have been prescribed bi-level or adaptive servo-ventilation therapy
- Are participating in another app-based research study
- Cannot participate for the full duration of the study (at least 90 days)
- Participants who have a medical history or concurrent illness that the investigator considers sufficiently serious to interfere with the conduct, completion, or results of this study, or constitutes an unacceptable risk to the participant for the duration of the study

3.6 SAMPLE SIZE

N= 300

A minimum total sample size of 270 patients, with 2:1 randomization (180 in Control group, 90 in Test group) is required to yield an 80% probability of detecting a difference of 0.8 hours in mean usage (160% of the minimally clinically significant difference) when the standard deviation is 2.5 and 2.0 in the Control and Test groups, respectively. The required sample size was calculated in the Two Sample T-Tests Assuming Unequal Variances Procedure using NCSS Power Analysis Statistical Software, Version 16 (PASS 16¹⁴) based on a one-sided, two sample t-test, using a significance level of 0.025.

Assuming a potential 10% drop-out rate due to study withdrawal or lost-to-follow-up, the final sample size will be 300 patients (270/0.9), equating to 200 in the Control group and 100 in the Test Group. The 2:1 randomization ratio was chosen because it is more cost-effective to enroll subjects in the control group.

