3.8 ANALYSIS POPULATIONS

Randomized Population: all participants enrolled and randomized to treatment groups.

Intent-to-Treat (ITT) Population: all participants randomized to control or intervention group, regardless of the actual intervention received.

Evaluable Population: all ITT subjects who complete the 90-day study period and complete the end-of-study questionnaire.

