3.9 DATA ANALYSIS

Baseline demographic and psychosocial factors will be summarized for each randomized group for ITT and Evaluable Populations. For continuous variables, such as age and PAP usage, the mean, standard deviation, median, and range will be presented. For categorical variables, such as gender, the number and proportion of participants in each category will be presented. Baseline demographics and psychosocial factors for the control and intervention groups will be compared with t-tests and Fisher's exact tests, as appropriate.

The primary analysis compares mean PAP usage at 90 days in the control and intervention groups using a two-way ANOVA on the ITT population. Randomization group and myAir usage (Yes/No) will be included as factors in the model. The interaction of the two factors will be considered, but will only be retained in the model if it is significant at the 5% level. Missing usage hours during a day will be imputed as 0 usage. A secondary analysis of mean PAP usage will be conducted using the Evaluable Population. A sensitivity analysis of the missing data assumption will be conducted by considering missing data as missing. In this analysis, participants with no usage data will be assumed to have a mean usage of 0 hours; other participants' mean usage will be calculated as the mean usage across nights for which there is data.

A subgroup analysis of the primary endpoint will be generated for patients who are identified as strugglers. A struggler is defined as a patient who uses their device for less than or equal to 3.5 hours/night during the first 3 days of usage. Mean PAP usage at 90 days will be compared in the control and intervention groups using a two-way ANOVA on the struggler population as described above. Descriptive statistics will also be presented for mean PAP usage, comparing strugglers and non-strugglers in control and intervention groups.

Adherence will be calculated for the ITT population from daily usage data using the Medicare definition for adherence (a patient is adherent if they use the device for more than 4 hours per night for 70% of the nights during the first 90 days of usage). Percent adherence will be compared between control and intervention groups using a logistic regression model on the ITT population. Randomization group, myAir usage, and the interaction of these two factors will be included in the model. Missing usage hours during a day will be imputed as 0 usage.

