4.4 REPORT OF DEVICE USAGE DATA

1. A report of PAP usage data (including average hours used per day, leak, pressure, and AHI) will be generated by the ResMed Data Analytics group at 90 days and 180 days and provided to the statistician for analysis.
2. A user-level analytics report of myAir engagement (including participants who registered for myAir and number of times they engaged with the app during the study) will be generated by the ResMed Data Analytics group at 90 days and 180 days and provided to the statistician for analysis.
3. A user-level analytics report of Restful engagement (including participants who registered for Restful and number of times they engaged with the app during the study) will be generated by Wellth at 90 days and 180 days and provided to the statistician for analysis.

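### Section 3.6 sizes the trial with an unequal-variance t-test, but the primary ANOVA in 3.9 pools the variance: a conservative mismatch costing about 4 points of power, with the 80% target still met at 300

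*Combined protocol and SAP*

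**What the plan says.** Section 3.6 gives "A minimum total sample size of 270 patients", split 180 control and 90 test, for 80% power to detect 0.8 h "when the standard deviation is 2.5 and 2.0 in the Control and Test groups, respectively". The method is the "Two Sample T-Tests Assuming Unequal Variances Procedure" in PASS 16, one-sided at 0.025. Dividing by 0.9 for 10% drop-out gives 300 (200/100), which section 3.3 sets as the enrolment ceiling.

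Section 3.9 compares mean usage at 90 days "using a two-way ANOVA on the ITT population". It adds: "Randomization group and myAir usage (Yes/No) will be included as factors in the model". The interaction stays only if significant at 5%. No unequal-variance or robust option is named, and no significance level or sidedness is given for the group effect.

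The ITT population in 3.8 is "all participants randomized to control or intervention group, regardless of the actual intervention received", and 3.9 fills gaps in the usage record: "Missing usage hours during a day will be imputed as 0 usage". Together these allow every randomised participant to be analysed.

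**The concern.** The plan expects unequal variances when it sizes the trial and drops that expectation when it analyses it. With equal arms, pooling would matter little. With 2:1 allocation it changes the standard error, and the direction depends on which arm is more variable. Here the arm with twice the participants has the larger SD, so the pooled standard error is too large.

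Part of the power the sample size would give under the test named in 3.6 is therefore not used, and the minimum of 270 describes a test that is not the primary one. The tolerance for under-recruitment also narrows, which matters because 3.3 gives only an upper limit on enrolment.

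**Working it through.** **Inputs.** From 3.6: difference d = 0.8 h, SDs 2.5 (control) and 2.0 (test), one-sided alpha 0.025, sizes 180/90 and 200/100. From 3.9: ANOVA on ITT. Assumptions: the 0.025 level also applies in 3.9; the SDs and the 0.8 h describe zero-imputed ITT usage, which 3.6 does not say; myAir has no effect on usage, and its uptake is similar in the two arms.

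**1. The plan's own figure.** The unequal-variance standard error at 180/90 is √(2.5²/180 + 2.0²/90) = √(0.03472 + 0.04444) = 0.2814 h. The noncentrality is 0.8/0.2814 = 2.843, with about 217 Satterthwaite degrees of freedom and a critical value of 1.971. Power from the noncentral t is 80.8%. The smallest exact 2:1 total reaching 80% is 267 (264 gives 79.9%), and 270/0.9 = 300. Section 3.6 reproduces.

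**2. Standard errors at 200/100.**
- True: √(6.25/200 + 4/100) = √0.07125 = 0.267 h.
- Pooled variance: (199 × 6.25 + 99 × 4)/298 = 5.503. Pooled standard error: √(5.503 × (1/200 + 1/100)) = 0.287 h.
- Ratio: 0.2873/0.2669 = 1.076.

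**3. Power of the pooled test when the SDs are 2.5 and 2.0.** The estimate varies with the true standard error, while the cut-off uses the pooled one: power ≈ Φ(d/SE_true − t × SE_pooled/SE_true).
- 200/100: Φ(0.8/0.2669 − 1.968 × 1.0763) = Φ(2.997 − 2.118) = Φ(0.879), about 81%.
- 180/90: pooled SE 0.3028, true SE 0.2814; Φ(2.843 − 1.969 × 1.0763) = Φ(0.724), about 76.5%.

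Integrating over both sample variances gives:

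| Analysed | Pooled (ANOVA) | Unequal-variance |
|---|---|---|
| 180/90 | 76.5% | 80.8% |
| 200/100 | 81.0% | 84.7% |
| Smallest 2:1 total for 80% | 294 (80.2%; 291 gives 79.7%) | 267 (80.4%) |

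With d = 0 the pooled test rejects with one-sided probability 0.0175, so a nominal 95% interval would cover 1 − 2 × 0.0175 = 96.5%. Simulating the ANOVA with a myAir factor (50% uptake, no myAir effect) gives 80.9% at 200/100 and 76.3% at 180/90.

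**4. Sensitivity to the SDs at 200/100.**
- Test SD 2.25 (assumption): SE ratio 1.036, power 77.5% pooled against 79.5%, a loss of 2 points.
- Equal SDs of 2.345 (assumption): 79.3% pooled against 79.2%, no loss. Both are below 80% because the test SD is larger, not because of pooling.

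**5. Sensitivity to myAir (all values assumed).**
- Uneven uptake, no myAir effect, 20,000 simulations per setting, ordinary ANOVA / HC3: 80.7% / 84.4% at 50% in both arms; 78.9% / 82.6% at 40% control and 60% test; 76.9% / 80.6% at 30% and 60%. The gap stays at 3.7 points.
- A real myAir difference of 1.0 h at 50% uptake, total SDs held: residual variances 6.25 − 0.25 = 6.00 and 4.00 − 0.25 = 3.75. The true SE is √(6.00/200 + 3.75/100) = 0.260 and the pooled SE √(5.2525 × 0.015) = 0.281. Power is about 82.9% pooled and 86.6% unequal-variance. Both rise and the gap remains.

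**The case against.** The best reply is that nothing is broken. Section 3.6 is correct for the procedure it names, sizing on a simpler test than the final model is common, and the planned ANOVA still exceeds 80% at 300 on the plan's own inputs. There is no false-positive risk. The single residual variance belongs to standard ANOVA and is not written in the plan. The loss also depends on planning SDs that may not hold for zero-imputed usage. All of that stands, and it is why the priority is minor. It does not remove the mismatch: the plan's own SDs are unequal, and one sentence recovers the power.

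A reader might go further and infer that the trial is underpowered. Three routes lead there, and none is supported.

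- Using the pooled SD of about 2.35 as if it were the true SD in both arms gives 79.3% at 200/100 and a minimum of 306. That ignores the smaller true standard error of 0.267 h, so it is not the test's actual power.
- Replacing 270 by 294 inside the drop-out sentence gives 294/0.9 = 327, above the ceiling of 300. That inflation is for participants lost from the analysis, whereas zero imputation allows all of them to stay in the ITT comparison.
- Uneven myAir uptake can take ordinary ANOVA below 80%, but it lowers the robust test about equally and the documents give no uptake figures. The cause would be correlation between group and myAir, not pooled variance.

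**Conclusion.** The mismatch is real and conservative. On the plan's SDs the pooled standard error at 200/100 is 7.6% too large, one-sided alpha is about 0.0175, and power is about 81.0% rather than 84.7%. The 80% target is met if all 300 are enrolled and analysed by ITT with zero imputation. With ordinary ANOVA the recruitment slack is 300 − 294 = 6 participants; with the unequal-variance test it is 300 − 267 = 33. If only 180/90 were analysed, ANOVA power would be 76.5%.

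These figures rest on the assumptions listed in the working, chiefly the planning SDs and the carry-over of the 0.025 level. The margin of 1 point over 80% is specific to no myAir effect and similar uptake; neither condition changes the comparison between the two tests. The documents do not support a claim of an underpowered trial, an inflated error rate or a need for more participants. Minor priority.

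**What to change.** In 3.9, state that the primary group comparison uses group-specific residual variances or HC3 robust standard errors, and that it is tested at one-sided 0.025 (two-sided 5%). This brings 3.9 into line with 3.6, leaves 270 and 300 valid, and gives about 84.7% power at 200/100. The cost is a sentence and, if the true SDs are equal, about half a point of power (simulated 78.8% with HC3 against 79.3% with ordinary ANOVA at a common SD of 2.345).

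If ordinary ANOVA is kept, do not simply exchange 270 for 294. Restate 3.6 as about 81% power with all 300 randomised participants in the zero-imputed ITT analysis, and 76.5% if only 180/90 are analysed. No extra enrolment is proposed either way.

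This does not endorse adjusting for myAir use. Section 4.4 has it reported at 90 and 180 days ("A user-level analytics report of myAir engagement"), so it may be measured after randomisation; that is a separate question.

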3.7 STUDY ENDPOINTS

Primary Endpoint: mean PAP usage at 90 days collected from participants' flow generators

Secondary Endpoints:

- Percentage of participants that meet the Medicare compliance standard (at least 4 hours per day on at least 70% of the days in a consecutive 30-day period any time in the first 90 days of therapy)
- Change in ESS and FOSQ-10 questionnaire scores
- Baseline scores of perceived disease severity, claustrophobia, coping skills, and health literacy as moderators of the intervention's effectiveness

3.8 ANALYSIS POPULATIONS

Randomized Population: all participants enrolled and randomized to treatment groups.

Intent-to-Treat (ITT) Population: all participants randomized to control or intervention group, regardless of the actual intervention received.

Evaluable Population: all ITT subjects who complete the 90-day study period and complete the end-of-study questionnaire.

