3.2 STUDY DESIGN

This is a prospective, randomized, two-arm, open-label study to evaluate effectiveness of applying financial and social incentives via a smartphone-based app in helping participants achieve adherence to therapy. Randomization will include an allocation ratio of 2:1 (control:treatment).

Two 'site to participant' contacts are required during this study. These contacts can either occur at the clinical site or remotely (e.g., by telephone). During the initial contact, their interest in the study and eligibility will be confirmed, then they will be consented, asked to complete the Baseline Questionnaire, and their demographic information will be collected on case report forms (CRFs).

Participants randomized to the intervention (Group B) will be provided with information and assistance in downloading Restful to their smartphone and registering with Wellth.

At the final contact (90 days), the participant will be asked to complete an End of Study Questionnaire and the investigative staff will collect PAP therapy data for the trial period and record it on CRFs. Participants in Group B will have access to the Restful app discontinued. This completes the participant's active participation in the study.

Daily usage data from AirView will be collected and transmitted electronically from usage initiation to 90 days, and then through 180 days.

Study data will be captured on CRFs. See **Appendix A** for the **Baseline and End of Study Questionnaires**. See **Appendix B** for **Participant Instructions** related to the study procedures and the Restful app.

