Mean change in ESS and FOSQ questionnaire scales will be compared between control and intervention groups using a mixed-effects linear model on the ITT population and a two-sample t-test on the Evaluable population. In the mixed-effects model, the response variable will be the mean questionnaire score and the model will include randomized group, visit, and a randomized group by visit interaction as fixed effects and subject as a random effect.

Baseline perceived disease severity, claustrophobia, coping skills, and health literacy will be tested as moderators of the intervention's effectiveness. Baseline scores will be regressed on the primary outcome (usage), and then in a mixed-effects model, the response variable will be usage and the model will include baseline score, randomized group, and a randomized group by baseline score interaction as fixed effects and subject as a random effect.

An exploratory analysis will examine how engagement with the study is associated with PAP usage. Engagement will be measured as app usage (number of touches). A linear regression model with PAP usage as the dependent variable and engagement as the independent variable will be fit to all ITT subjects (engagement is zero for all control subjects). An exploratory analysis will also test whether the intervention has a direct or indirect effect on the following psychosocial factors: the pros and cons of change, self-efficacy, and social support. Finally, an exploratory analysis will test whether nomination of, and the extent of engagement with, a social support person moderates the intervention effectiveness.

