4.2 INITIAL (ENROLLMENT) CONTACT

1. Provide patient with access to informed consent document.
2. When consent has been obtained, collect device information (device ECN, device settings, mask type), demographic, and baseline data into the electronic data capture (EDC) system.
3. Randomize participant in EDC.
 - a. Participants randomized to the Control group (Group A) will complete a set of baseline questionnaires.
 - b. Participants randomized to the Treatment group (Group B) will complete a set of baseline questionnaires and provided with instructions to download Restful to their smartphone.
 - c. Monitor both groups' PAP device usage per your standard of care.

[figure not shown]
4.3 90-DAY STUDY CONTACT

1. Both Group A and Group B will be asked to complete a set of end of study questionnaires. Restful will be 'turned off' for Group B participants.
2. Continue to monitor participants' PAP device usage per your standard of care.
3. Distribute compensation for study participation.

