5.2 AIRVIEW

AirView is the HIPAA compliant web-based system that is routinely used for telemonitoring. The PAP device contains built in wireless connectivity which transmits data via a mobile network to a secure data center. Data is transmitted at the completion of each period of use (e.g. after each night of use). Data can then be accessed, via a login code, by the respiratory/sleep team to assess items such as device efficacy (residual AHI), mask leak, and usage hours.

AirView is compliant with HIPAA, EU 95/46/EC, and national privacy laws. Data are encrypted and all database accesses are logged and can be re-traced.

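### The secondary analysis of device-recorded PAP usage keeps only questionnaire completers: a minor, avoidable selection after randomization, confined to one supportive analysis

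*Combined protocol and SAP*

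**What the plan says.** Section 3.8 gives a single Evaluable Population: "all ITT subjects who complete the 90-day study period and complete the end-of-study questionnaire". Section 3.9 uses it for two different kinds of outcome:

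- Usage: "A secondary analysis of mean PAP usage will be conducted using the Evaluable Population".
- Change in ESS and FOSQ: "a two-sample t-test on the Evaluable population", alongside a mixed model on ITT.

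The primary endpoint in section 3.7 is "mean PAP usage at 90 days collected from participants' flow generators", and its primary analysis is done "using a two-way ANOVA on the ITT population", with missing daily hours set to 0. On capture, section 3.2 states: "Daily usage data from AirView will be collected and transmitted electronically from usage initiation to 90 days, and then through 180 days". Section 5.2 adds that the device sends its data wirelessly after each use. The questionnaire comes at the 90-day contact (section 4.3): "Both Group A and Group B will be asked to complete a set of end of study questionnaires". No separate evaluable set for usage is defined, and section 3.8 does not say what completing the 90-day period means in terms of device data.

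**The concern.** For ESS and FOSQ the questionnaire is the outcome, so requiring it makes sense. For usage it contributes nothing to measurement: the hours reach AirView whether or not the participant fills in a form. Nor does it act as a per-protocol rule, since it does not require onboarding to Restful or any use of the app.

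Its effect on the usage analysis is to leave out participants whose usage is fully known, because of something they did or did not do about 90 days after randomization. If completers and non-completers use PAP differently, and completion differs between arms, the contrast is no longer a randomized comparison. The arms are open-label and only one of them receives an app, so a difference in completion is possible. The Evaluable result could then disagree with ITT because of who answered the form rather than because of the intervention. Precision is also lost on data already collected.

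**Working it through.** **1. The plan's own figure.** Section 3.6 gives a difference of 0.8 h, SDs of 2.5 h (Control) and 2.0 h (Test), one-sided alpha 0.025, 2:1 allocation and 80% power. I used the unequal-variance t-test (noncentral t, Satterthwaite degrees of freedom), with

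SE = √(2.5²/n_C + 2.0²/n_T) and noncentrality = 0.8/SE.

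At 180/90, SE = √(0.03472 + 0.04444) = 0.281, noncentrality = 2.84 and power = 80.8%. The smallest 2:1 design reaching 80% is 178/89 = 267. The stated 270 is therefore reproduced, and 270/0.9 = 300. The sample size is not in error; it only serves to scale what follows.

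**2. Loss of precision.** The 10% allowance in section 3.6 covers withdrawal and loss to follow-up; it does not mention questionnaire non-completion. The documents give no completion rate, so the rates below are assumed. They are the share of all randomized participants who meet the Evaluable definition, taken as equal in both arms.

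| Share evaluable | Control/Test | SE (h) | Power at 0.8 h |
|---|---|---|---|
| 100% | 200/100 | 0.267 | 84.7% |
| 90% | 180/90 | 0.281 | 80.8% |
| 80% | 160/80 | 0.298 | 76.0% |
| 70% | 140/70 | 0.319 | 70.3% |
| 60% | 120/60 | 0.345 | 63.5% |

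The first row assumes device data for all 300. If the planned 10% withdraw, a usage set without the questionnaire condition sits on the second row.

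**3. Bias.** Let p be the completion rate in an arm and g the completers' mean usage minus the non-completers'. The arm mean is p × (completers' mean) + (1 − p) × (non-completers' mean), so the completers' mean exceeds it by (1 − p) × g. With the same g in both arms, the Test-minus-Control difference among completers departs from the all-randomized difference by

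bias = (1 − p_T)g − (1 − p_C)g = g × (p_C − p_T).

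The documents give neither p nor g. Assumed values, in both directions:

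| g (h) | Control / Test completion | Bias (h) |
|---|---|---|
| 1 | 85% / 75% | 1 × 0.10 = +0.10 |
| 1 | 80% / 90% | 1 × (−0.10) = −0.10 |
| 2 | 85% / 75% | 2 × 0.10 = +0.20 |
| 2 | 75% / 90% | 2 × (−0.15) = −0.30 |
| 3 | 85% / 75% | 3 × 0.10 = +0.30 |
| 3 | 75% / 90% | 3 × (−0.15) = −0.45 |

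The range is 0.10 to 0.45 h in size. Section 3.6 calls 0.8 h 160% of the minimally clinically significant difference, which implies 0.8/1.6 = 0.5 h as the minimal difference.

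Equal completion gives zero bias only when g is the same in both arms. At 80% completion in each arm, with g of 1 h in one and 2 h in the other, the bias is 0.20 × (2 − 1) = 0.20 h.

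**The case against.** The strongest reply is that no main conclusion rests on this set. The primary usage analysis and the Medicare adherence analysis are on ITT, and neither the missing-data sensitivity analysis nor the struggler analysis is tied to the questionnaire. Participants who skip the form stay in all of those. A reader might infer that the trial discards their data or that its primary result is biased; the text supports neither. This part of the reply stands and fixes the severity as minor.

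A reader might also infer that completion is likely to be higher in the Test arm, which would bias the contrast downwards. The documents do not support that. The app's reminder concerns using therapy, the $75 depends on onboarding and nights of at least 4 hours, and the social content is tied to streaks or general encouragement. Nothing in the app prompts or rewards the questionnaire. At day 90 both groups are asked to complete it, and study compensation is not limited to one arm. Completion may differ; its direction is unknown.

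Two further replies carry less weight. Section 3.9 summarizes baseline factors for both ITT and Evaluable participants, so some selection would be visible, though not selection on usage itself. And one completer set lets usage and ESS/FOSQ be read on the same patients. That is a reasonable convenience, and the definition is not an internal contradiction, but it does not need to be the only evaluable analysis of usage.

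**Conclusion.** The point holds as a minor one. The questionnaire condition is unnecessary for device-recorded usage, leaves out data already collected, and selects participants after randomization. It affects only the secondary Evaluable analysis of usage; the ITT primary result does not change.

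The size is illustrative. A bias of 0.10 to 0.45 h in either direction rests on an assumed gap of 1 to 3 h, common to both arms, and an assumed 10 to 15 point difference in completion. The upper end is more than half the 0.8 h design difference and close to the implied 0.5 h minimal difference; the lower end is small. The power figures of about 76% and 70%, against about 85% with all 300, rest on the design SDs, a two-sample t-test rather than the planned ANOVA, and equal completion in both arms.

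**What to change.** In section 3.8, split the definition:

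- **Usage:** ITT participants who did not withdraw before day 90, with no questionnaire condition. Keep those who stopped using PAP and count their nights without data as 0, under the rule already in section 3.9. This also settles what completing the 90-day period means for usage.
- **ESS/FOSQ t-test:** keep the present definition, including the questionnaire.

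Do not replace the questionnaire condition with a requirement for usage records through day 90. Data are sent after each use, so a participant who abandons therapy may produce no further records; read literally, that requirement would select on the outcome itself.

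In section 3.9, label the evaluable usage result as supportive of ITT, and report the number excluded from each set, with reasons, by arm.

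The cost is a few sentences and a second evaluable set to describe. The usage set still conditions on not withdrawing, which also happens after randomization, so it reduces the selection without removing it.
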